Appendix B: Acute Rhinitis Symptoms Severity Questionnaire (English version)

Please, tick the box that corresponds to your child's situation

Not sick □	A little sick □	Sick □	Very sick □	
Q2-Q7: How do you evaluate the intensity of the following symptoms of your child?				
Symptoms	Not present	mild	moderate	severe
Runny nose				
Stuffy nose/blocked nose				
Yellow/green discharge				
Nasal crust (dr mucus)	y 🗆			
Sore throat (hurts to swallow)				
Sneezing/cough				
Q8-Q10: How do you evaluate the impact of the common cold on your child's activities? Activity No impact Mild impact Severe impact impact				
Sleeping				
O.CCP.I.D				
Breathing			 	†

Appendix C: Primary Notification Form

This form is to be completed immediately and no later than 24h (in case of any SERIOUS safety issue) or 48h (in case of any NON-SERIOUS safety issue).

Protocol title:	Acronym:	
Sponsor code:	Site number: Country:	
Competent authority(ies) reference number:	Transmission date:	
	ddmmyy	
1. Date, type and classification of incident Incident codification: First notification		
Date of the incident	 	
bute of the meldent	ddmmyy	
Reporter awareness date	ddmmyy	
incident threat Death	ublic health Unanticipated serious deterioration in state of health Non serious incident undesirable	
2. Patient information Birthdate:	Gender: Male Female	
mmyyyy	Unknown	
Height:	Non applicable	
cm cm cm	Weight: Weight:	
List any of the patient's prior condition of medi	cation that may be relevant to this incident:	
3. Medical Device information		

UDI device identifier /	Basic UDI-DI/E		UDI production identifier:
Eudamed ID: not applicable	not applica	ible	not applicable
Medical device name (L		 
proprietary or common name) & SKU:			
Class of risk:			
Batch number			
Expiry date (yyyy/mm):			
Other details:			
4. Incident information			
Intended use of the medica	l device:		
Date of first use:			ddmmyy
Date of last use:			ddmmyy
Frequency of use:			
Description of the incident: Provide a comprehensive description of the incident, including (1) what went wrong with device (if applicable) and (2) a description of health effects (if applicable), i.e. clinical signs, symptoms):			
Outcome & Health Impact:			
 ☐ death ☐ life threatening ☐ hospitalization (initial or prolonged) ☐ required intervention to prevent permanent damage ☐ disability or permanent damage ☐ congenital abnormality/birth defect 			
no serious outcome			
other, please specify:			
Remedial actions taken by i	nvestigator, pat	ient, or user subsec	quent:

Version 1.1 –2023.02.02 Study Number: LPH-2202

5. Reporter information	
☐ Distributor	
☐ Patient	
☐ Healthcare professional:	
\square Investigator (in case of the safety issue has been occurred du	uring a clinical investigation)
☐ Other, please specify:	
For any follow-up please kindly indicate the contact de	etails:
Name and Surname	
Name and Surname:	
Email:	
Phone number:	
Fax:	
	-
Date:	Signature:

Appendix D: SAE form

This form is to be used when a causal relationship between the serious adverse event and the additional investigational procedure is suspected (art 80.5 and 80.6).

This form is to be completed immediately and no later than 3 days after the investigation site personnel have been made aware of the event and sent immediately to the Clinical Study Monitor by mail [contact] and [name] , to BG ClinicalS [contact], FAX: no [contact] and to the sponsor [contact] and/or [contact] (as back-up method) and to the Vigilance Manager [name] ([contact]) and the EU representative ([contact]).

Protocol title:		Acronym	: BASICC	
Efficacy and safety of Healsea® Babykids in the				
treatment of acute infectious rhinitis symptoms in				
children				
Sponsor code: LPH-2202		•	nt Authority	(ies) reference
		number:		
		Site numl		
Transmission date: ddm	nmyy	Country:	Bulgaria	
SAE#				
(to be completed by the First notification:	: 🗌	Follo	w-up: 🗌	Final:
sponsor)				
1. Subject information				
Birthdate: mmyyyy	Gende	er: Male 🗌	Female	Other 🗌
Height: cm Wei		Weight:, Kg		
				¬
Investigational arm:test groupcompariso		parison groupblinded		
2. Description of the SAE				
The serious adverse event resulted in:	Me	dical or su	urgical inter	vention to prevent
		ife threatening illness or injury or permanent		
_ , , , , , , , , , , , , , , , , , , ,		mpairment to a body structure or a body		
· · · · · · · · · · · · · · · · · · ·		function		
, , , , , , , , , , , , , , , , , , , ,		Chronic disease		
		Foetal distress, foetal death or congenital		
		hysical or mental impairment or birth defect		
Permanent impairment to a body structure				
or a body function				
Description of the SAE: (if clinical nature, indicate	the diag	nosis or th	ne major syn	nptoms)

Date of the procedure lea	ding to the SAE:				ddmmyy
SAE onset date:			ddr	nmyy	not capture
SAE stop date:			ddr	nmyy	on going
Or date of death if SAE "fa	atal"		ddr	nmyy	
Summary description (study procedure, significant medical history, progression of event, available laboratory results, study procedure):					
(*) Except hospitalisation study participation	s with durations	and goal planr	ned in the pro	otocol o	r scheduled before
3. Mesures taken fo	llowing the SAE				
The event led to: Prescription of correct	tive or symptoma	tic medication	/ medical dev	ice (spe	cify name, dosage):
Other,specify:				••••••	
Other,specify:					
## Other, specify: ## Outcome Not recovered/Not resolved visequelae Fatal: in case of death	vith 🔲 Unkno		_		ed/Resolved
4. Outcome Not recovered/Not res Recovered/Resolved v	vith 🔲 Unkno	own	_		
## A. Outcome Not recovered/Not result in case of death	vith Unkno , has an autopsy b ality assessment v	een conducted	i? 	Yes 🗌 N	
4. Outcome Not recovered/Not res Recovered/Resolved v sequelae Fatal: in case of death	vith Unkno , has an autopsy b ality assessment v	een conducted	i? 	Yes	No

Enclose in the notification the results of carried out examination, reports of hospitalisation, etc...

6. Submitter information	
☐ Investigator	
☐ Other, please specify:	
Name:	
e-mail:	
Phone number:	
Fax:	
Date:	ddmmyy
Signature:

2. STUDY OBJECTIVES

2.1. Primary objective

The primary objective is to assess the efficacy of **Healsea® Babykids** on the overall health status score of the Acute Rhinitis Symptoms Severity Questionnaire (ARSSQ) in 2-6 years old children during a treatment period of 7 to 10 days as compared to Placebo.

2.2. Secondary objectives

The secondary objectives are:

- To assess the impact of **Healsea® Babykids** on the duration of each infectious rhinitis symptom and on quality of life as compared to Placebo;
- To assess the impact of **Healsea**[®] **Babykids** on the intake of conventional common cold medications (antibiotics, antipyretics, mucolytics, decongestants, antitussives, systemic and topical corticosteroids) as compared to Placebo;
- Safety: to assess systemic and local tolerance of **Healsea**® **Babykids** over the study period.

3. STUDY DESIGN

This is a prospective, interventional, double-blinded, placebo controlled, randomized, national (Bulgaria), multicentre PMCF study.

The study comprises two parts:

- Part 1 (D1-D11): treatment of the acute phase, with **Healsea**® **Babykids** or with **isotonic nasal spray** (**Placebo**), 2 puffs in each nostril 2 times per day with a minimum of 7-day-treatment period (14 intakes of the investigational device) up to 10 days (20 intakes of the investigational device);
- Part 2 (up to D15/D18): follow-up phase.

Investigational plan description (see Figure 1):

- Visit 1 (V1) – (Day 1): Screening/Inclusion/Randomization

Information and provision of the information sheet to legal guardians/parents of participants, consent signature, demographic data and medical history, ongoing medication, inclusion/non-inclusion criteria, physical and clinical examination, baseline assessment of the ARSSQ, randomization, diary presentation, treatment dispensation of **Healsea**® **Babykids** Nasal Spray or **Placebo (Isotonic nasal spray)** (according to randomization list).

AXIODIS CRO 7/47

D1-D8 up to D1-D11 (at home):

Daily completion of the paper diary (questionnaire, adverse events/incidents and concomitant medications), Healsea® Babykids / Placebo nasal spray treatment daily administration.

Between D8 and D11 (at home):

End of Healsea® Babykids / Placebo nasal spray treatment.

Up to D15/D18 (at home):

Daily completion of the diary (adverse events/incidents, concomitant medications, ARSSQ if applicable, until the patient feels not sick for two consecutive days).

Visit 2(V2) - (Day 15-18): end of study

Diary review, reporting of the adverse events/incidents, compliance, ARSSQ completion if "not sick" is not ticked for two consecutive days in the previous days.

The maximal study duration for each patient is 18 days.

	Acute p	Acute phase Follow-up phas		phase
Visit name	Screening/Inclusion	At home	At home	End of study
Visit Number	V1		***************************************	V2
Days	D1	D1 to D11	D12 to End of study	D15-D18
Informed consent	х			
Eligibility criteria	х			
Demography and Medical history ***	x			
Physical and clinical examination	х			x
Baseline assessment of the Acute Rhinitis Symptoms Severity Questionnaire	х			
Ongoing medication	x			
Randomization	х			
Treatment (Healsea® Babykids or Placebo)	Х*	Χ#		
Subject paper diary (Acute Rhinitis Symptoms Severity Questionnaire**)				
Adverse events/incidents and concomitant medication reporting				
Compliance				x

Figure 1: Flow chart of the study

AXIODIS CRO 8/47

^{*} Treatment dispensation

** ARSSQ to be completed with the investigator on site at screening and at the end of the study if the patient still has symptoms ("not sick" not ticked for 2 consecutive days in the previous days). After day 8, until complete resolution of symptoms for 2 consecutive days (question 1 of the questionnaire).

[#] Treatment from D1 to D8 and up to D11.
*** Medical History - Relevant medical history in connection to infectious acute rhinitis, allergic rhinitis, nasal disorders and asthma back to 2 years

4. SAMPLE SIZE

This is a PMCF study. The primary endpoint is a customized symptom and quality of life questionnaire. An arbitrary cohort of 200 children has been chosen. A cohort of 100 children in the Healsea® Babykids arm and 100 children in the Placebo arm is anticipated to allow to demonstrate the interest of using Healsea® Babykids in the acute infectious rhinitis. Indeed, 100 patients by arm are enough to detect a Cohen's effect size of 0.4 with a power of 80% and a type I error of 5%. Cohen's effect size is defined as the standardized difference between area under the curve (AUC) in groups. According to Cohen's methodology, 0.4 is an intermediate size between a small effect (0.2) and a medium effect (0.5) and is coherent with the expected result. The Placebo arm will be used as the reference group.

Study Number: LPH-2202

BASICC

The recruitment will be performed using a 1:1 randomization ratio.

5. DEFINITION OF THE ANALYSIS SETS

Enrolled patients: all patients whose parents/legal guardians signed an informed consent.

Included patients: all the enrolled patients who participated in the study.

Randomised patients: all the included patients who were assigned a treatment number.

Safety population: all the randomised patients who used the nasal spray at least once.

Full Analysis Set (FAS): all the patients from the Safety population and with at least one postbaseline efficacy data.

Any patient not satisfying major entry criteria or for whom post randomisation data are not available will be identified by the Validation Committee during the data review, and could be excluded from the FAS in agreement with circumstances exposed in the ICH-E9 §5.2.1.

Per Protocol (PP) Set: Efficacy population based on the FAS without patients with major protocol deviations.

The status of protocol deviations (minor or major) will be validated during the data review meeting.

Safety endpoint will be performed on the Safety Set.

The analyses of primary and secondary endpoints will be performed on the FAS.

The primary and one secondary (modelling of AUC on global ARSSQ score by multivariate ANCOVA) endpoints will also be analysed on the PP set, analyses on the PP set being supportive in superiority trials.

AXIODIS CRO 9/47

6. STATISTICAL METHODS

6.1. Data processing

The analyses will be computed with SAS Version 9.4 TS Level 1M6 Copyright (c) 2016 by SAS Institute Inc., Cary, NC, USA.

6.2. Description

The number of available data and the number of missing data will be given and the following descriptive statistics will be provided:

- For quantitative parameters: mean, standard deviation, median, Q1, Q3, extreme values (min and max).
 - In this case, calculated statistics (mean, standard deviation, median, Q1, Q3) will generally be displayed with one more significant figure than the observed data, unless the described variable necessitates less precision.
- For qualitative parameters: number and percentage of each modality.
 Usually, one decimal digit will be given. A second decimal digit could be provided to improve the display, if required.

6.3. Statistical/Analytical issues

6.3.1. Significance level

All statistical analyses will be performed at the 0.05 global significance level (type I error rate), using two-sided tests.

The statistical results will only allow to conclude on the primary efficacy criterion. All other statistical results have to be considered within a descriptive perspective and not as inferential issues. No adjustment for Type I error will be done. P-values of statistical tests on secondary criteria will be provided for information only.

6.3.2. Interim analysis

No interim analysis will be performed.

6.3.3. Multiplicity

There is only one main efficacy criterion and no comparative testing will be performed, then multiplicity adjustments are not needed.

6.3.4. Multicentre studies and Adjustment for covariates

No adjustment on centre will be performed.

AXIODIS CRO 10/47

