7.1.2 Measures to be taken to minimize or avoid bias

Randomization:

The random product attribution will be performed after checking that the eligibility criteria are fulfilled, thus minimizing the selection bias. Each site will receive several treatment blocks in accordance with the randomization table generated by Axiodis (blocks of 4). During the V1 visit, the investigator will deliver a product (active or placebo) to the patient in chronological order using the list of treatments allocated to the respective site. This method allows to maintain the 1:1 balance in a multicentric study.

Example: the site 01 received 3 treatment blocks, i.e. 12 treatments, number 001 to 012. For the patient 01-001, the investigator will deliver the treatment 001. The site 02 received 3 treatments blocks, i.e 12 treatments, number 013 to 025. For the patient 02-001, the investigator will deliver the treatment 013.

Blinding and unblinding:

The randomization list will be drawn up using a validated software and before the beginning of the study, by a statistician (at Axiodis) not involved in the study. The master randomization list will be stored confidentially until the study blind is broken at the end of study.

The randomization list will be:

- Transmitted by the Axiodis statistician to the person in charge of the product preparation,
 Creapharm
- Uploaded into the patient unblinding module of the eCRF

During the whole study and in the absence of unblinding, neither the investigators nor the subjects nor the staff involved (CRO, sponsor...) will be aware whether the product is Healsea® Babykids or the Placebo. Every effort will be made to maintain the blind during the study as well as during the follow-up period.

Both Medical Devices (Healsea® Babykids and Placebo) will be indistinguishable: same aspect, same packaging and same labelling of the vials.

The unblinding will occur after the database locking, at the end of the study. The statistician responsible for the randomization list will be in charge of the unblinding.

Emergency Unblinding:

In case of a medical emergency where knowledge of the blinded treatment is necessary for the treatment of an adverse event/incident, the investigator shall perform the unblinding via the unblinding module of the eCRF. The investigator shall send an e-mail informing about the unblinding with patient ID, date and reason of unblinding (the name of patient not to be communicated for GDPR compliance) to:

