7.1.7 Investigation sites: number, location

The clinical investigation will be conducted in 8 sites in Bulgaria. All investigators are familiar with acute infectious rhinitis and study procedures.

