The investigator will provide the parents/legal guardians with the device according to the site specific treatment list, in order to respect the 1:1 randomization (blocks of 4). The investigator will explain how to use it.

NB: The first use of the device will be performed in the evening of the Day 1.

D1-D8 up to -D11 (at home):

The Parent/legal guardian will be asked to complete the ARSSQ in the diary, once daily in the evening. The symptoms occurring from the morning to the evening should be taken into consideration. The ARSSQ shall be scored at least from D1 to D8. Adverse events/incidents and concomitant medications are to be reported during the whole period

Between D8 and D11 (at home):

End of Healsea® Babykids/Placebo nasal spray.

➤ NB: The last study nasal spray intake will be performed **between D8 and D11** in the morning. The patient should stop taking the investigational device before D11 only if the question 1 "not sick" of the ARSSQ is ticked YES for 2 consecutive days.

Up to D15/D18 (at home):

Parents/legal guardians will continue to complete the paper diary daily (incidents/adverse events/expected undesirable sides effects, concomitant medications). For patients for whom common cold symptoms persist, parents/ legal guardians will be instructed to continue to complete the ARSSQ, until the subject feels not sick for two consecutive days.

Visit 2 (V2) - (Day 15-Day 18): end of study

The investigator or his/her delegated designee will:

- Perform a physical and clinical examination.
- Collect the patient diary.
- Review the paper diary to validate adverse events pertinent in the context of the common cold, incidents linked to medical device use and concomitant medications reported by the parents/legal guardians. Complete the e-CRF accordingly and report any new relevant safety events
- Ask parents/legal guardians to complete the ARSSQ if the patient still has symptoms.
- Assess the compliance to the treatment by weighing the device bottle returned by the parents/legal guardians. If a nasal spray is not returned or lost, the investigator will ask the

Version 1.1 –2023.02.02 Page **37** of **64**

Study Number: LPH-2202

parents/legal guardians to specify the number of missed nasal spray uses and will report the data into the e-CRF.

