8.3 Primary endpoint

In order to analyze the primary endpoint, a multivariate regression model of the AUC of the global score of the ARSSQ during the first 11 days will be used.

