10. EFFICACY

10.1. Analysis of the primary efficacy criterion

The primary objective will be analysed by performing a t-test (or a Wilcoxon test if the normality assumption is not acceptable) on the means of AUC on global score of ARSSQ during the first eleven days of the study between treatment groups.

The answers of the ten items of ARSSQ are scored from 0 to 3 (0: negative answer; from 1 to 3: positive answer with an increasing severity level). See the daily report in appendix (§13.3). The global ARSSQ score at each time point is the sum of the scores to the ten items of the ARSSQ:

At each time point t: ARSSQTOT(t) =
$$\sum_{j \text{ in } \{1; ...; 10\}} ARSSQ_j(t)$$

AUC of global ARSSQ score will be computed by the method described in §6.4.7.

Patients will be analysed on the FAS and the PP Set. In each case, boxplots of the AUC on global score will be realized by treatment group. The number of available data and the p-value will be printed on the figure.

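### The primary AUC test ignores site although treatment is allocated in blocks of 4 within 8 sites; if sites differ, the test is conservative and forgoes some power (minor efficiency point)

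*SAP*

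**What the plan says.** Allocation is organised by site. Protocol 7.1.2 says: "Each site will receive several treatment blocks in accordance with the randomization table generated by Axiodis (blocks of 4"), and the investigator hands out products in order from the list for that site. Protocol 7.4.1 repeats that parents are provided "with the device according to the site specific treatment list, in order to respect the 1:1 randomization (blocks of 4"). Protocol 7.1.7 gives the number of sites: "The clinical investigation will be conducted in 8 sites in Bulgaria".

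The analysis does not use site. SAP 6.3.4 says only: "No adjustment on centre will be performed". SAP 10.1 analyses the primary objective by "performing a t-test (or a Wilcoxon test if the normality assumption is not acceptable) on the means of AUC". The candidate covariates for the secondary models in SAP 10.2 are baseline temperature and baseline items 2 to 7 of the questionnaire, so no planned analysis includes site.

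SAP section 4 states that 100 children per arm give 80% power for an effect size of 0.4 at a 5% type I error, and adds: "Cohen's effect size is defined as the standardized difference between area under the curve (AUC) in groups". SAP 6.3.1 limits inference to one test: "The statistical results will only allow to conclude on the primary efficacy criterion".

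**The concern.** When treatment is balanced within site by design, a difference in mean AUC between sites adds almost nothing to the variance of the treatment difference. A two-sample test does not know this. It estimates its error from all variation within an arm, including that between sites. Its standard error is then too large, its true type I error is below 5%, and it has less power than an analysis that includes site.

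Site differences are plausible. The questionnaire is non-validated and completed by parents (Protocol 7.1.3), the investigator rates the severity needed for entry (Protocol 7.3.1.1, 7.4.1), and many symptomatic medicines are permitted (Protocol 7.4.2.1), so local prescribing habits can affect scores. The documents do not quantify any of this, and the true effect may be nil.

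What is at stake is power for the one test on which the SAP allows a conclusion.

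**Working it through.** **Inputs from the documents.** Effect size d = 0.4, 100 per arm, power 80%, type I error 5% (SAP 4); two-sided tests (SAP 6.3.1); 8 sites (Protocol 7.1.7), hence 200 / 8 = 25 children per site on average; blocks of 4 within site (Protocol 7.1.2).

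**Assumption.** The share of AUC variance lying between sites (ICC) is not in the documents. I use 0, 0.05, 0.10 and 0.20, with the total SD set to 1.

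**Step 1: reproduce the plan's figure.** n per arm = 2 × (1.960 + 0.842)² / 0.4² = 98.1, rounded up to 99. The noncentral t gives 99.08, so 100. Power at 100 per arm is Φ(0.4 / √(2/100) − 1.96) = Φ(2.828 − 1.96) = 80.7%, or 80.4% by noncentral t. The stated figure holds and contains no site term.

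**Step 2: approximation with perfect balance within site.** The true SE of the treatment difference is √(2(1 − ICC)/100), while the t-test works with about √(2/100). Hence:
- t-test type I error ≈ 2 × [1 − Φ(1.96 / √(1 − ICC))]
- t-test power ≈ Φ((2.828 − 1.96) / √(1 − ICC))
- site-model power ≈ Φ(2.828 / √(1 − ICC) − 1.96)

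At ICC 0.10 these give 2 × [1 − Φ(2.066)] = 3.9%, Φ(0.915) = 82.0% and Φ(2.981 − 1.96) = 84.6%.

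**Step 3: simulation.** 40,000 trials per setting, 8 sites of 25, permuted blocks of 4 within site with an incomplete last block allowed, normal site effects and residuals. Monte Carlo SE is about 0.1 point for type I error and 0.2 for power.

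| Assumed ICC | Type I error, t-test | Mean SE, t-test / site model | Power, t-test | Power, site model | Gain (points) |
|---|---|---|---|---|---|
| 0 | 5.0% | 0.1412 / 0.1413 | 80.3% | 80.3% | 0 |
| 0.05 | 4.6% | 0.1408 / 0.1377 | 81.2% | 82.3% | about 1 |
| 0.10 | 4.1% | 0.1404 / 0.1341 | 82.1% | 84.5% | about 2.5 |
| 0.20 | 3.2% | 0.1395 / 0.1265 | 83.6% | 88.4% | about 5 |

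Type I error with site in the model stays at 4.9 to 5.1%. The t-test's SE is larger by 0, 2, 5 and 10% (for example 0.1404 / 0.1341 = 1.047). A second simulation of 20,000 trials per setting agrees: power 81.0 vs 82.3%, 81.8 vs 84.2% and 83.4 vs 88.2% at ICC 0.05, 0.10 and 0.20.

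**Step 4: uneven recruitment.** With sites of 60/44/32/24/16/12/8/4 and the smallest joined to the next, power is 80.5 vs 80.4%, 81.2 vs 82.3%, 82.5 vs 84.6% and 84.1 vs 88.3%. The conclusion does not depend on equal sites.

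**Step 5: Wilcoxon branch.** Plain Wilcoxon against the site-stratified (van Elteren) test, 8 sites of 25: 78.5 vs 77.2%, 79.4 vs 79.5%, 80.0 vs 81.4% and 81.5 vs 85.7%. Stratifying costs about 1 to 2 points if sites do not differ, breaks even near ICC 0.05 and gains above that. These figures use normal data, whereas the branch applies when normality fails, so they are indicative only. The 78.5% at ICC 0 has nothing to do with site, since sites do not differ there.

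**The case against.** The strongest reply is that nothing in the plan is wrong. The SAP addresses centre adjustment and states a choice. The unadjusted test does not inflate type I error, a significant result stands, and the gain rests on an ICC that the documents do not give and that could be zero. All sites are in one country under one protocol. On the Wilcoxon branch the remedy can lose a little. All of this stands, and it is why the point is minor.

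Timing also counts. The SAP is marked final on 9 August 2023, the study was planned to start in February 2023 and last 4 months, and SAP section 12 already cites answers that patients gave. That section also records one change to the primary test, so this would be a second. This stands too, and the fix depends on whether unblinding has occurred.

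A reader might infer that the unadjusted test drops below the planned 80% power once sites differ. That would follow only if 0.4 were expressed in units of the within-site SD. The documents do not support this. SAP section 4 standardises the difference between the treatment groups, the ordinary SD within an arm includes variation between sites, and 100 per arm reproduces from the plain two-sample formula. On that scale the t-test keeps at least about 80% at every ICC tried.

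The objection does not supply a reason for leaving site out, and for the linear model including it costs no measurable power even when sites do not differ.

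**Conclusion.** The point holds as a minor efficiency improvement. The trial balances treatment by site and then does not use site in its one inferential test. If mean AUC differs between sites, the t-test is conservative, and the power forgone is about 1 point at ICC 0.05, 2.5 at 0.10 and 5 at 0.20; nothing is lost at ICC 0. These figures rest on assumed ICCs, a normal outcome, 200 analysed children and an effect size in units of the total SD. They are a range, not a forecast.

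Validity is not threatened, and the planned power is not undermined at full enrolment.

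**What to change.** **If treatment has not been unblinded**, change the primary AUC analysis only:

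- SAP 6.3.4: state that the primary analysis of AUC includes site because treatment is allocated in blocks within site, and that other analyses are not adjusted for centre. Very small sites are combined with the next smallest, decided on total counts while blinded, with the same groups used for the PP Set. A threshold must be named; fewer than 8 FAS children (two full blocks) is my suggestion and does not come from the documents.
- SAP 10.1: compare AUC with a linear model with treatment and site as fixed effects, and report the adjusted difference versus Placebo, its 95% CI and the two-sided p-value. If normality of the residuals is not acceptable, use the van Elteren test. Keep the unadjusted test as a sensitivity analysis.
- Add the matching rows to Mock T13, print the primary p-value on the boxplots, and record and date the change in SAP section 12.

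**If unblinding has already taken place**, keep the unadjusted test as primary, state why centre was left out, and add the site model as a sensitivity analysis.

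**Cost.** No new data are needed, since the subject identifier contains the site number (Protocol 7.4.1). The model uses 7 degrees of freedom (198 to 191; critical t 1.9720 to 1.9725). The Wilcoxon branch carries the loss of about 1 to 2 points if sites do not differ. The change also brings the primary test back to the type of analysis in Protocol 8.3, where "a multivariate regression model of the AUC of the global score of the ARSSQ during the first 11 days will be used", although the protocol names no covariates and so lends only limited support. The secondary models are descriptive under SAP 6.3.1 and need no change.
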